## 6. ADVERSE EVENTS: LIST AND REPORTING REQUIREMENTS

Adverse event (AE) monitoring and reporting is a routine part of every clinical trial. The AEs and the characteristics of an observed AE (Section 6.2) will determine whether the event requires expedited reporting **in addition** to routine reporting.

All subjects who receive at least one dose of study treatment will be valid for the safety analysis.

All observations pertinent to the safety of the study treatment will be recorded and included in the final report.

Safety variables include the following: AEs, laboratory changes (complete blood counts, electrolytes, chemistry, and coagulation), changes in vital signs (blood pressure, heart rate, respiratory rate, and temperature) and ECG and, in some instances, changes in chest x-ray images, as produced at the investigator's discretion (e.g., for evaluation for pneumonia).

AEs evaluation will be continued after the first 2 cycles.

### 6.1 Adverse Events and Risks List

For this study, the applicable reference document is the most current version of the investigator's brochure (IB), summary of product characteristics, and/or package insert.

Overview listings of frequent events that have occurred so far in the clinical development are shown in the current IB. The investigator will routinely review any new distributions of the IB for relevant new safety information and incorporate into the informed consent form document as appropriate.

### 6.2 Definitions

Adverse event: Any untoward medical occurrence associated with the use of a drug in humans, whether or not considered drug related.

Life-threatening adverse event or life-threatening suspected adverse reaction: An adverse event or suspected adverse reaction is considered "life-threatening" if, in the view of the investigator, its occurrence places the patient at immediate risk of death. It does not include an adverse event or suspected adverse reaction that, had it occurred in a more severe form, might have caused death.

Serious adverse event or serious suspected adverse reaction: An adverse event or suspected adverse reaction is considered "serious" if, in the view of the investigator, it results in any of the following outcomes: death, a life-threatening adverse event, inpatient hospitalization or prolongation of existing hospitalization, a persistent or significant incapacity or substantial disruption of the ability to conduct normal life functions, or a congenital anomaly/birth defect. Important medical events that may not result in death, be life-threatening, or require hospitalization may be considered serious when, based upon appropriate medical judgment, they

may jeopardize the patient and may require medical or surgical intervention to prevent one of the outcomes listed in this definition. Examples of such medical events include allergic bronchospasm requiring intensive treatment in an emergency room or at home, blood dyscrasias or convulsions that do not result in inpatient hospitalization, or the development of drug dependency or drug abuse.

*Suspected adverse reaction:* Any adverse event for which there is a reasonable possibility that the drug caused the adverse event. For the purposes of IND safety reporting, "reasonable possibility" means there is evidence to suggest a causal relationship between the drug and the adverse event. Suspected adverse reaction implies a lesser degree of certainty about causality than adverse reaction, which means any adverse event caused by a drug.

*Unexpected adverse event or unexpected suspected adverse reaction:* An adverse event or suspected adverse reaction is considered "unexpected" if it is not listed in the investigator brochure or is not listed at the specificity or severity that has been observed; or, if an investigator brochure is not required or available, is not consistent with the risk information described in the general investigational plan or elsewhere in the current application, as amended. For example, under this definition, hepatic necrosis would be unexpected (by virtue of greater severity) if the investigator brochure referred only to elevated hepatic enzymes or hepatitis. Similarly, cerebral thromboembolism and cerebral vasculitis would be unexpected (by virtue of greater specificity) if the investigator brochure listed only cerebral vascular accidents. "Unexpected," as used in this definition, also refers to adverse events or suspected adverse reactions that are mentioned in the investigator brochure as occurring with a class of drugs or as anticipated from the pharmacological properties of the drug, but are not specifically mentioned as occurring with the particular drug under investigation.

### **6.3 Reporting adverse events to the responsible IRB**

In accordance with applicable policies of the University of Pittsburgh Institutional Review Board (IRB), the Investigator will report, to the IRB, any observed or volunteered adverse event that is determined to be 1) *associated with the investigational drug or study treatment(s)*; 2) *serious*; and 3) *unexpected*. Adverse event reports will be submitted to the IRB in accordance with the respective IRB procedures.

Applicable adverse events will be reported to the IRB as soon as possible and, in no event, later than 10 calendar days following the investigator's receipt of the respective information. Adverse events which are 1) *associated with the investigational drug or study treatment(s)*; 2) *fatal or life-threatening*; and 3) *unexpected* will be reported to the IRB within 24 hours of the Investigator's receipt of the respective information.

Follow-up information to a reported adverse event will be submitted to the IRB as soon as the relevant information is available. If the results of the Investigator's follow-up investigation show that an adverse event that was initially determined to not require reporting to the IRB does, in fact, meet the requirements for reporting; the Investigator will report the adverse event to the IRB as soon as possible, but in no event later than 10 calendar days, after the determination was made.

## **7. REGORAFENIB INFORMATION**

A list of the adverse events and potential risks associated with the investigational agent administered in this study can be found in Section 6.1.

### **7.1 Drug information**

Regorafenib 40-mg tablets contains regorafenib and the inactive excipients microcrystalline cellulose, croscarmellose sodium, magnesium stearate, povidone, colloidal anhydrous silica, polyvinyl alcohol-part hydrolyzed, talk, titanium dioxide E171 (color index 77891), Macrogol/PEG 33350, lecithin (soy), iron oxide yellow – E172 (color index 77491), iron oxide red – E172.

Regorafenib tablets will be packaged in high density polyethylene bottles with a white child resistant closure and induction seal. Each bottle includes 30 tablets and a 3-gram desiccant. The bottles will have a label affixed containing study identification, product identification, and quantity of tablets. Once the drug has been received it must be kept in a secure, dry location. Study drug must be stored in its original bottle at a temperature not above 25°C (77°F).

The study drug must be exclusively used for the investigation specified in this protocol and it will only be accessible to authorized staff.

Regorafenib will be provided by Bayer as 40-mg tablets, which are coated, not divisible, gray-orange-red, oval (length 16 mm, width 7 mm, thickness 4.9-5.6 mm), and 472 mg each in total weight. Tablets are in an immediate-release dosage form with rapid dissolution characteristics under the *in vitro* test conditions.

### **7.2 Ordering and accountability**

All study drugs will be stored in Investigational Drug Services in accordance with Good Clinical Practice (GCP) and Good Manufacturing Practices (GMP) requirements and/or institutional standard operating procedures.

### **7.3 Destruction and return**

At the end of the study, unused supplies of regorafenib should be destroyed according to institutional policies. Destruction will be documented in the Drug Accountability Record Form. The certificate of destruction should be sent to Bayer.

A completed “Unused Study Drug Disposition Form Destruction or Return Confirmation” should be sent to Bayer at the following address:

E-mail: [contact]

OR

[contact]

OR

Mail: (VP of Medical Affairs named in contract) at  
Bayer HealthCare Pharmaceuticals  
[name]  
[name]

## **8. SPECIAL STUDIES**

Archival tissue specimens that were collected at time of diagnosis may be requested and used for correspondence molecular analyses, including: EGFR pathway genes, VEGFRs, PDGFR, and C-Met.

### **8.1 Pathology Material**

Tissue specimens will be analyzed for the mutational status of EGFR, K-RAS and B-RAF. All testing will be performed as done for clinical samples in the Molecular Pathology Laboratory at the University of Pittsburgh Medical Center (UPMC). Tissue specimens, including formalin fixed paraffin embedded (FFPE) tissue blocks, or cell blocks, with representative tumor tissue, preferably from resection or core biopsy specimens, will be obtained from the site where the diagnostic material was collected. If tumor tissue or cell blocks are not available, unstained slides (a minimum of 20) will be requested. DNA sample preparation from microdissected tumor areas will follow standard techniques for DNA extraction using DNeasy Blood & Tissue Kits (Qiagen, Inc). Detection and quantitation of mutations in codons 12, 13 and 61 of K-RAS, and detection of the hotspot transversion mutation T1799A that causes the amino acid substitution V600E in BRAF will be performed by pyrosequencing analyses using the PyroMark Q24 (Qiagen, Inc). PCR and sequencing methods will be used for detection of the E19del and L858R mutations in the EGFR gene. Expression levels of EGFR will also be evaluated by immunohistochemistry with the EGFR pharmDx™ Kit (Dako, Inc). VEGFR, PDGFR and C-Met analyses will be performed based on UPMC pathology standard methods.

Analysis of these samples may take place while the patient is receiving study treatment, but the results will not be communicated to the subject. The results will be used in the analysis of the final study data.

## 9. STUDY CALENDAR

Baseline evaluations are to be conducted within 14 days prior to start of protocol therapy. Scans and x-rays must be done 28 days prior to the start of therapy. In the event that the patient's condition is deteriorating, laboratory evaluations should be repeated within 48 hours prior to initiation of the next cycle of therapy.

There is a window of  $\pm 1$  week available for scheduling treatment and/or procedures at the discretion of the Investigator/Sub-investigator. This applies also if a course is missed or a subject's treatment and/or testing day(s) need to be rescheduled due to the subject's inability to comply with the study calendar (i.e., hospitalizations, business, vacation plans, travel from long distances for study treatment, in advance of the scheduled date to allow ready access to the result(s), reduce financial burden on the subject [i.e. non-UPMC insurance coverage] or reduce travel inconvenience, illness, transportation issues, holidays, family emergencies, etc.).

	Screening	Day 1 (Cycles 1&2)	Day 8 (Cycles 1&2)	Day 15 (Cycles 1&2)	Day 22 (Cycles 1&2)	Day 1 (Cycle 3+)	End of Treatment d	Follow up e
History and Physical	X	X				X	X	
Weight	X	X				X	X	
Vital Signs h			X	X	X			
Performance Status	X	X	X	X	X	X	X	
Adverse Event Assessment	← →							
Con meds		X	X	X	X	X	X	
Urine protein/Creatinine	X							
Pregnancy test a	X							
Blood tests b	X	X	X	X	X	X	X	
PT/INR and PTT c	X							
CEA, CA19-9 i		X				X	X	
Tumor Measurement (CT or MRI C/A/P)	X					X f	X	
Regorafenib g		X	X	X		X		

Archived Tissue Sample Collection	X							
Disease status and survival								X e

- a. WOCBP only, 7 days prior to the start of study drug
- b. Blood tests include: CBC with diff, platelets, Bilirubin, Alk Phos, AST, ALT, Total Protein, Albumin, Sodium, Potassium, Blood Glucose, Calcium, Phosphate, Magnesium, BUN/Creatinine, no need to repeat if done within 3 days of cycle 1 day 1.
- c. PT/INR and PTT will be done for everyone at screening visit. For patients on anticoagulation therapy, it should be done weekly while on the study drug.
- d. To occur 28 days ( $\pm$  5 days) after the last dose of the study drug
- e. The follow-up for survival will be every 3 months (+/- 4 weeks) by review of medical records, or direct contact patient contact.s.
- f. Up to 3 days before day 1 of every odd cycle.
- g. 3 weeks on 1 week off. Patient to keep a drug diary and return diary and pill bottle day 1 of every cycle.
- h. If clinically significant toxicity exists then patient to see MD for physical exam.
- i. CEA, CA19-9 to be obtained prior to the start of study drug.

Note: Starting day (day1) of the subsequent cycles may be delayed up to 1 week to accommodate the patients/physicians clinic needs.

## 10. MEASUREMENT OF EFFECT

### 10.1 Antitumor Effect Measurement

For the purposes of this study, patients will be re-evaluated for response every 2 cycles(up to 3 days before day 1 of every odd cycle). In addition to a baseline scan, confirmatory scans should also be obtained following initial documentation of objective response.

Response and progression will be evaluated in this study using the international criteria proposed by the revised Response Evaluation Criteria in Solid Tumors (RECIST) guideline (version 1.1) [Eur J Ca 45:228-247, 2009]. Changes in the largest diameter (unidimensional measurement) of the tumor lesions and the shortest diameter in the case of malignant lymph nodes are used in the RECIST criteria.

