#### 10.1.5 Duration of Response

Duration of overall response: The duration of overall response is measured from the time measurement criteria are met for CR or PR (whichever is first recorded) until the first date that recurrent or progressive disease is objectively documented (taking as reference for progressive disease the smallest measurements recorded since the treatment started).

The duration of overall CR is measured from the time measurement criteria are first met for CR until the first date that progressive disease is objectively documented.

Duration of stable disease: Stable disease is measured from the start of the treatment until the criteria for progression are met, taking as reference the smallest measurements recorded since the treatment started, including the baseline measurements.

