#### 10.1.6 Progression-Free Survival

**PFS is defined as the duration of time from start of treatment to time of progression or death, whichever occurs first.**

#### 10.1.7 Response Review

All responses will be reviewed by PI and, simultaneous review of the patients’ files and radiological images.

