## **12. STATISTICAL CONSIDERATIONS**

### **12.1 Data Analysis Plan**

#### **12.1.1 Primary objective**

Evaluate the progression-free survival (PFS) of patients with advanced biliary cancer who had failed first-line chemotherapy when receiving regorafenib. The progression-free survival function will be estimated by the Kaplan-Meier method, with a 90% confidence interval. The estimated median PFS will be derived from the estimated progression free survival function. The null hypothesis that the median PFS is 2.0 months or less (see Justification of Design, below) will be tested using the two-sided 80% confidence interval around the median PFS. If the left side of the confidence interval does not include two months, the null hypothesis will be rejected ( $\alpha=0.10$ ).

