### **12.2 Justification of Design**

The primary objective for this study is to evaluate the median progression-free survival (PFS) in patients with advanced or metastatic biliary tract carcinoma/cholangiocarcinoma treated with

regorafenib monotherapy. The monthly accrual is 2 patients, and it is assumed that accrual will require 19 months, and that the analysis will be performed 9 months after the last patient is put on study (that is, at month 28, patients who have not progressed will be treated as censored). A median PFS of 3.5 months or greater will be taken as evidence of activity in this patient population. The null hypothesis to be tested is that the median PFS is 2.0 months or lower. If the maximum of 37 patients is accrued, the study will have 83% power (using a one-sided test with  $\alpha=0.10$ ) if the alternative hypothesis that median PFS for patients in this population treated with regorafenib is at least 3.5 months is true.

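### The first tumour scan follows cycle number and falls days before the 2.0-month boundary of the primary test, so permitted scheduling slips can date scan-detected progression after it

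*Combined protocol and SAP*

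**What the plan says.** **Scan timing.** Section 10.1 says "patients will be re-evaluated for response every 2 cycles(up to 3 days before day 1 of every odd cycle", and note f of the study calendar (section 9) repeats it: "Up to 3 days before day 1 of every odd cycle". Cycles last 28 days (section 4).

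**Permitted slippage.** Section 9 gives a window of plus or minus one week, "available for scheduling treatment and/or procedures at the discretion of the Investigator/Sub-investigator". A note under the calendar adds: "Starting day (day1) of the subsequent cycles may be delayed up to 1 week to accommodate the patients/physicians clinic needs".

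**Endpoint.** Section 10.1.6 defines PFS as the "duration of time from start of treatment to time of progression or death, whichever occurs first". It does not say how scan-detected progression is dated or what happens when a scan is late. The nearest convention is the one for response duration in section 10.1.5, which runs "until the first date that recurrent or progressive disease is objectively documented".

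**Test.** Section 12.2: "The null hypothesis to be tested is that the median PFS is 2.0 months or lower". Section 12.1.1 uses the two-sided 80% confidence interval for the median: "If the left side of the confidence interval does not include two months, the null hypothesis will be rejected". No conversion from days to months is given for PFS. The trial has one arm and no control (Synopsis).

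**The concern.** The decision date lies about a week after the first scheduled look at the tumour, and the plan's own scheduling allowances span that gap. A patient whose progression is found only at a first scan done on day 61 or later counts as progression-free at 2.0 months. The same patient scanned on time counts as an event.

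The error runs one way. Progression found at an early scan is already an event before the boundary, so early scans do not compensate for late ones. There is no concurrent arm on the same schedule to absorb the shift. At stake is whether the primary result partly reflects clinic scheduling.

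**Working it through.** **Inputs.** N = 37, null median 2.0 months, alternative 3.5 months, one-sided alpha 0.10, stated power 83% (section 12.2); 80% interval rule (section 12.1.1); scan due 0 to 3 days before cycle 3 day 1 (sections 9 and 10.1). Assumptions: 30.44 days per month, no censoring before 2.0 months, exponential PFS where a curve is needed.

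**1. The plan's power.** Testing that the median exceeds 2.0 months amounts to testing that the event-free proportion at 2.0 months, S, exceeds 0.5. Under the alternative S = 2^(−2/3.5) = 0.673, with standard error √(0.673 × 0.327 / 37) = 0.0771. Power = Φ(0.173/0.0771 − 1.282) = 83.2%. The stated 83% reproduces and is not in dispute.

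**2. The cut-off.** Lower 80% limits for S:

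| Event-free | plain | log | log-log | exact |
|---|---|---|---|---|
| 22/37 | 0.491 | 0.4997 | 0.484 | 0.476 |
| 23/37 | 0.519 | 0.527 | 0.511 | 0.503 |

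All four reject from 23 of 37. P(Bin(37, 0.5) ≥ 23) = 0.094; exact power at S = 0.673 is 0.80. Under the null the count is exactly 22 with probability 0.068.

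**3. Dates, in days elapsed from treatment start.** Cycle 3 day 1 is 2 × 28 = 56, so the scan is due on day 53 to 56. The boundary is 2 × 30.44 = 60.9, and the first day beyond it is 61.
- Due day 56: a slip of 61 − 56 = 5 days crosses; one full week gives day 63.
- Due day 53: 61 − 53 = 8 days are needed; one full week gives day 60 and does not cross. Crossing needs both cycle 2 and cycle 3 to start late, or a cycle delay added to the procedure window.

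**4. Illustrative effect.** Let L be the number of first scans done after the boundary, and s the share of pre-boundary events found only at that scan. Take S = 0.5 with on-time scans, and lateness unrelated to outcome. Then alpha = P(X + Y ≥ 23), where X ~ Bin(37 − L, 0.5) and Y ~ Bin(L, 0.5 + 0.5s).

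| L | s = 10% | 25% | 40% | 60% |
|---|---|---|---|---|
| 2 | 0.100 | 0.108 | 0.117 | 0.129 |
| 4 | 0.105 | 0.124 | 0.144 | 0.174 |

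**5. A rough ceiling for s.** Section 2.1 gives second-line median OS of 4 to 6 months. If OS is exponential, deaths by day 53 are 1 − 2^(−53/(4 × 30.44)) = 26% down to 1 − 2^(−53/(6 × 30.44)) = 18% of patients. Events by the boundary are 50% under the null, so s is at most 1 − 0.26/0.5 = 48% to 1 − 0.18/0.5 = 64%.

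**6. What on-time scanning leaves.** If the 2.0-month median refers to true progression and every scan is done on day 56, progressions arising between then and day 60.9 are dated to the next scan. With all events scan-detected, recorded S = 2^(−56/60.88) = 0.529 and alpha = 0.166. With 40% scan-detected, alpha is about 0.12.

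**The case against.** The size rests on two shares that the documents do not give: how many first scans run late, and how many early events only that scan would reveal. With two late scans and s up to 40%, alpha is 0.100 to 0.117, and part of that rise only uses up the slack between 0.094 and 0.10. This stands; the figures illustrate and do not predict.

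The benchmark is itself loose. Section 2.1 puts second-line median PFS or time to progression at 1.6 to 2.3 months, a spread of 0.7 × 30.44 = 21 days against a slip of 5 to 8. Those medians presumably came from scans too. If they already contain similar slippage, there is no inflation. The scan schedules behind them are not given, so this cannot be settled either way.

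The calendar note on cycle starts may merely restate the one-week window. On that reading a scan due on day 53 never crosses, but one due on day 54 or later still can.

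Three stronger readings do not hold. A reader might set s = 100% and infer an alpha of 0.243 with four late scans; deaths and progressions found off-schedule keep their own dates, and the OS in section 2.1 makes that an implausible extreme. The 12-week life expectancy equated with 3 months might suggest a 28-day month and a boundary on day 56, the scan day itself; that is a rounded eligibility criterion, not a PFS convention. And the fact that one event can reverse the result at 22 of 37 is true of any threshold; it needs that exact count and a late scan in the right patient.

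**Conclusion.** The concern holds in a limited form. The first scan is due shortly before the date on which the primary test turns, permitted slips can carry it past that date, the effect favours rejection only, and no rule in sections 10.1.6 or 12.1.1 absorbs it. A few late-dated progressions could matter at a cut-off of 23 of 37.

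The size is uncertain: alpha of about 0.10 to 0.17 for 2 to 4 late scans and s of 10 to 60%. This assumes a 30.44-day month, no early censoring, progression dated at the scan, and a 2.0-month null that refers to PFS recorded with on-time scans. The documents do not show that the error rate is in fact inflated. The case for acting is that the bias runs one way at the primary decision point and can be removed by wording.

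**What to change.** 1. **Study calendar note f and section 10.1:** schedule tumour scans every 8 weeks by calendar from cycle 1 day 1, regardless of cycle number or delays. Give the first scan its own window that closes before the 2.0-month boundary (for example day 53 to 60 at 30.44 days per month), exempt from the general one-week window.
2. **Sections 12.1.1 and 12.2:** state the number of days in a month and that progression is dated when documented. If a shorter month is chosen, set the first-scan window to match.
3. **Reporting:** give the number of first scans done after the window beside the primary result.

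An interval-censored sensitivity analysis is optional. Dating late scans back to the scheduled day should be dropped or left optional, because it can count a progression that arose after the boundary as an event before it.

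**Cost:** wording only, with no added patients or scans. The cut-off and the on-time alpha of 0.094 are unchanged. Some scans will not coincide with cycle day 1. The change does not remove the residual in step 6 of the working, and a first scan that still misses its window would still be dated late, which is why item 3 is needed.
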